# 3.0 Number of Participants

**Primary Objective:** We plan to enroll 220 individuals over the course of two years to participate in the pilot intervention, with approximately equal numbers of men and women

Page 8 of 37 Revised: February 16, 2023

**Secondary Objective:** We will obtain administrative records for approximately 20,000 individuals who are released from prison between 1/1/2020 – 12/31/2023 to characterize trends in non-emergency outpatient health care use for the overall population of incarcerated persons in Wisconsin.

3.1 If applicable, distinguish between the number of participants who are expected to be enrolled and screened and the number of participants needed to complete the research procedures (i.e., numbers of participants excluding screen failures).

# 4.0 Feasibility & Acceptability

# **Primary Objective:**

We estimate based on analyses completed in Phase 1 that approximately 70% of people incarcerated at the two participating institutions meet eligibility criteria. We plan to meet and discuss the study with every eligible individual, as described below, and anticipate that approximately 70% of eligible individuals will agree to participate. Taking this into consideration, we assume 50% of all people who are being released from the institutions will enroll in the study.

We will strive to enroll the 220 participants in the two-year study period or about 9 people per month. We will be enrolling men from Oakhill Correctional Institute (OCI) and women from Wisconsin Women's Correctional System (WWCS).

Due to high volume of potentially eligible individuals, and feasibility of resources for the Nurse Case Manager, potential participants who have anticipated releases to Dane or Milwaukee County will be prioritized in recruitment.

Participants will be considered enrolled after signing the consent form. Active participation in the study will continue until the end-of-study assessment, which will be scheduled to occur 3 months after the date of release from prison. Participants may voluntarily withdraw from the study at any time.

We anticipate that the recruitment goals will be feasible to achieve, based on the annual number of individuals released from the two participating institutions, as shown below.

E	Eligibility				
	Oakhill	REECC	Total		
Total Yearly Average Releases (2019-2022)	316	327	643		
Total Released to Dane and Milwaukee Counties	112	65	177		
Total Released to Rock, Racine, Kenosha, and Waukesha Counties	62	64	126		
Assumed enrollment of eligible individuals (50%)	87	64	151		
Monthly Enrollment Possible	7	5	12		
Total Recruitment Possible (24 months)	168	120	288		

**Secondary Objective:** Preliminary assessment of effectiveness

We will conduct a descriptive analysis of concurrent trends in outpatient health care use among formerly incarcerated adults, focusing on those with a history of a substance use disorder, HCV or HIV. Each year, approximately 9,000 individuals >=18 years are released from Wisconsin state correctional facilities. Based on our prior work, we expect that 70% of these individuals will have one or more of these three conditions. Thus, we expect the population-based analysis will include approximately 20,000 individuals who were released between 1/1/2020-12/31/2023.

Page 9 of 37 Revised: February 16, 2023

# 5.0 Inclusion and Exclusion Criteria

5.1 Describe how individuals will be screened for eligibility. If you plan to retain screening data collected by phone or other methods for people who decline to participate, describe this, including the rationale for retaining the information.

People who will be included in the study sample for the pilot intervention is as follows:

- Adults 18 years of age or older,
- · Able to understand and speak in English,
- Plans to reside in Wisconsin after release,
- Eligible for Wisconsin Medicaid and willing to enroll prior to release,
- Has a history of one or more of the following: current HIV infection, current or past HCV infection, substance use disorder by self-report.

For our **primary objective**, using existing WIDOC resources, we will obtain a rolling list on a weekly basis of individuals who will be released in the next 6 months from each of the 2 institutions. For everyone on the list, the Nurse Case Manager will complete an initial eligibility assessment by reviewing:

- Anticipated release date (must be within 6 months of review);
- The electronic health record (any positive test or prior treatment for HIV or hepatitis C, or current or previous medications for substance use disorder);
- And results of COMPAS assessments, which include specific criteria for "probable need for SUD services".

Regardless of evidence of potential eligibility in the EMR or COMPAS review, all individuals releasing within the next 6 months will be sent recruitment letters, offered information about the study, and be invited to screen with the Nurse Case Manager or assisting study team member. The Nurse Case Manager or assisting team member will use a simple screening tool to determine if the interested individual meets all eligibility criteria in order to enroll in the study. [See Eligibility Screener Document]

We plan to retain all screening information from individuals if they are not eligible or decide not to enroll in the study for the purpose of retrospectively identifying characteristics of eligible versus ineligible or uninterested participants that could bias our study sample.

5.2 Describe the criteria that define who will be excluded from your final study sample.

Study exclusion criteria for the **primary objective** is as follows:

- Unable to provide informed consent form or impaired ability to make decisions
- Planned discharge to another correctional facility or other carceral setting (e.g. release to jail or immigration detention center)
  - 5.3 If any specific population (e.g., racial/ethnic group, sex or gender) will be targeted or excluded, describe this and provide justification.

No specific racial/ethnic group will be targeted. We intend to recruit equal numbers of men and women in the study.

5.4 Describe how individuals will be screened for eligibility. If you plan to retain screening data collected by phone or other methods for people who decline to participate, describe this, including the rationale for retaining the information.

# **Primary Objective:**

People that meet the following criteria will be included in the sample for our feasibility and acceptability analysis:

Page 10 of 37 Revised: February 16, 2023

- Adults 18 years of age or older,
- Able to understand and speak in English,
- Eligible for Wisconsin Medicaid and willing to enroll prior to release,
- Has a history of one or more of the following: current HIV infection, current or past HCV infection, substance use disorder by self-report.

# **Secondary Objective:**

People that meet the following criteria will be included in the sample for our population-based analysis:

- Adults 18 years of age or older,
- Enrolled in Medicaid within one-month of release,
- Has a history of one or more of the following: current HIV infection, current or past HCV infection, identified need for substance use related services based on COMPAS assessment.

We will use several data sources to determine if individuals meet the inclusion criteria (see "Aim 3 Secondary Objective Data.docx"): Wisconsin DOC administrative, COMPAS, and prescription medication data; Wisconsin Medicaid enrollment data; WEDSS surveillance data; and the Wisconsin State Lab of Hygiene.

5.5 Describe the criteria that define who will be excluded from your final study sample.

After application of the inclusion criteria, there are no additional exclusion criteria.

5.6 If any specific population (e.g., racial/ethnic group, sex or gender) will be targeted or excluded, describe this and provide justification.

No specific racial/ethnic group will be targeted.

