# State the hypotheses to be tested.

The main hypothesis to be tested in this pilot study is that the CJC-TraC protocol developed in collaboration with WIDOC partners will be successfully implemented in a way that is deemed acceptable to WIDOC staff and incarcerated patients. We will consider implementation to be successful if (1) we enroll a substantial number of eligible participants (e.g. at least 50% of the targeted sample size of 220), and (2) Participants complete post-incarceration study activities with a reasonable rate of retention (e.g. fewer than 50% of participants being lost to follow-up after

release). We will assess acceptability by systematically querying study participants and WIDOC staff about their experience with CJC-TraC using validated questionnaires, as described below.

A secondary hypothesis is that individuals who participate in the CJC-TraC pilot will have a higher rate of using non-emergency, outpatient health services (e.g. primary care clinic appointment) after incarceration, in comparison to contemporaneous rates of health service utilization by individuals with comparable levels of comorbidities and demographic characteristics.

2.2 Define the primary and secondary study endpoints. A study endpoint is a specific measurement or observation to assess the effect of the study variable (study intervention). Study endpoints should be prioritized and should correspond to the study objectives and hypotheses being tested.

In this pilot study we will assess endpoints related to feasibility, acceptability, and effectiveness, as described above:

Primary Endpoints: Feasibility

- The number of participants who are enrolled and complete the baseline study assessment per month, at each of two institutions;
- The number of pre-release CJC-TraC intervention sessions completed with the nurse case manager for each participant, at each institution;
- The number of post-release telephone contacts between the CJC-TraC nurse case manager and study participants;
- The proportion of study participants who are retained in follow-up for three months and complete the end-of-study assessment.

Primary Endpoints: Acceptability

- The proportion of study participants who rated specific aspects of the intervention useful and encounter volumes appropriate, collected on 3 month survey.
- The subjective experience in the program regarding prison-to-community transition support and healthcare support, collected by participant interview.

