**Secondary Objective:** applicable. The inclusion criteria include individuals >=18 years of age released from prison in the study years who are enrolled in Medicaid for at least one month. We neither prioritize nor exclude the adult groups identified above. We defined the inclusion criteria to accomplish the research objective: to describe the contextual trends in health care use among the population, from which intervention participants are selected. Safeguards are in place to protect the privacy and confidentiality of subjects as described in the UW IRP data security and monitoring plan (Appendix 11).

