**Secondary Objective:** We will gather preliminary evidence regarding the effectiveness of CJC-TraC for improving the rate of outpatient care utilization by examining the trends in health care use among the overall population from which CJC-TraC participants were recruited. The population-level trends serve as the counterfactual, the observed trends in health care use among individuals who were plausibly eligible for, but did not receive, the CJC-TraC intervention. We will use a retrospective cohort study design to describe post-release health care use among individuals who meet the sample criteria noted in 5.4. Results from this aim, will inform the interpretation of our findings from the Primary Objective including whether and to what extent we observe indications of intervention effectiveness (per deviations of post-release health care use among intervention participants from population-based trends).

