# 20.0 Study Analysis

20.1 Statistical Hypotheses: State the formal and testable null and alternative hypotheses for primary and key secondary endpoints, specifying the type of comparison (e.g., superiority, equivalence or non-inferiority, dose response) and time period for which each endpoint will be analyzed.

**Primary Objective:** The main hypothesis to be tested in this pilot study is that the CJC-TraC protocol is feasible and acceptable to WIDOC staff and incarcerated patients.

**Secondary Objective:** The secondary objective is descriptive and not hypothesis driven. The objective is to describe secular trends in health care use among the population from which CJC-TraC participants were recruited. These trends provide a counterfactual regarding what we observe in the absence of the intervention.

Page 31 of 37 Revised: February 16, 2023

20.2 Sample Size Justification: Include number of participants to recruit, screen, and enroll to have adequate power to test the key hypotheses for the study. Include anticipated impact of dropout/withdrawal/cross-over rates, missing data, etc. on study power. Provide all information needed to validate your calculations.

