The proposed sample size was chosen by considering what would be an appropriate case load and frequency of client interactions for the Nurse Case Manager. This level was informed by focus group data collected in Phase 1 and input from collaborators, and eligible participants at the two correctional institutions where the study will occur. Publicly available data from the Department of Corrections indicates that Oakhill Correctional has approximately 316 annual releases while Robert E. Ellsworth Correctional Center (REECC), a facility in the Wisconsin Women's Correctional System (WWCS), has approximately 327, for a total of 643 annual releases at the two study sites. There are 112 and 65 people released to Dane and Milwaukee counties annually at Oakhill and REECC respectively, for a total of 177. These counties will be prioritized for recruitment. An additional 126 individuals released annually to Rock, Waukesha, Racine, and Kenosha counties, 62 from Oakhill and 64 from REECC. These counties can be adequately serviced by the NCM at this time, and the number of serviceable counties will increase throughout the intervention. Assuming that 50% of people incarcerated at the two facilities and releasing to a serviceable county will be eligible and enroll in the study, we would expect a total of 168 participants at Oakhill Correctional Institution and 120 at REECC over the 24-month study period, for a total of 288 total participants. Our recruitment goal is 220 individuals.

20.3 Participant Population(s) for Analysis: Identify and describe the analysis datasets (e.g., which participants/populations will be included in each).

The dataset construction begins with all individuals released from a WI state correctional facility between 1/2020-12/2023. From this universe of individuals, we will apply the sample criteria noted in 5.4 to generate the analytic dataset: adults who have a history of, or living with, SUD, HCV or HIV and enroll in Medicaid within the month of release.

20.4 Statistical Methods: Summarize the overall statistical approach to the analysis of the study data.

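### The cohort called the counterfactual is not built as the contemporaneous, comparable, untreated group that Sections 2.1 and 13.1 describe, and no participant-versus-cohort contrast is specified

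*Combined protocol and SAP*

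**What the plan says.** **What is promised.** The secondary hypothesis in Section 2.1 is that participants will use more non-emergency outpatient care "in comparison to contemporaneous rates of health service utilization by individuals with comparable levels of comorbidities and demographic characteristics". The secondary-objective paragraph of Section 13.1 describes the population trends as those of "individuals who were plausibly eligible for, but did not receive, the CJC-TraC intervention", and says the results will show whether there are "indications of intervention effectiveness (per deviations of post-release health care use among intervention participants from population-based trends". Section 20.1 labels the objective descriptive but adds: "These trends provide a counterfactual regarding what we observe in the absence of the intervention".

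**What is built.** Section 20.3 starts from "all individuals released from a WI state correctional facility between 1/2020-12/2023". Section 5.4 then requires age 18 or over, Medicaid enrollment within a month of release, and HIV, HCV or a COMPAS-identified substance use need. Section 5.5 closes the list: "After application of the inclusion criteria, there are no additional exclusion criteria". The Medicaid rule appears in two other forms: "who are enrolled in Medicaid for at least one month" in Section 6.3 and "enroll in Medicaid within the month of release" in Section 20.3.

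**What is analyzed.** Section 20.4 compares characteristics and outcomes across study years and fits regressions for change over time, with individual and area-level covariates. It mentions no comparison of participants with the cohort.

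**The concern.** If participants' visit rates are set against this cohort and the gap is read as Section 13.1 intends, the gap reflects who was recruited as well as what the program did. Section 1.2 reports that women, and White individuals compared with Black individuals, are more likely to have a visit within 30 days. The pilot aims for about equal numbers of men and women and gives priority to two counties, so its mix on known predictors need not match that of statewide releases. Section 2.1 says these preliminary effectiveness data will be used to plan later formal studies, so a misread gap would carry forward into that planning.

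**Working it through.** **1. The two groups side by side**

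| Feature | Pilot participants | Population cohort |
|---|---|---|
| CJC-TraC | Received | Enrollees who meet the rules are not removed (5.5, 20.3) |
| Released from | Two institutions; Dane and Milwaukee Counties prioritized (4.0) | Any state facility (20.3) |
| Substance use | Self-report (5.1) | COMPAS-identified need (5.4) |
| Medicaid | Eligible and willing (5.1) | Actually enrolled (5.4) |
| Planned carceral discharge | Excluded (5.2) | Not excluded (5.5) |
| Language and residence | English; plans to live in Wisconsin (5.1) | No such rule |
| Sex mix | About equal (3.0, 5.3) | As released |
| Entry | Consent and nurse capacity (7.3, 8.1) | Administrative records |

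These differences need not act in one direction. Requiring actual enrollment could raise the cohort's recorded use. Keeping people bound for other custody could lower it. The documents size none of them, so no net sign follows.

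**2. The plan's own cohort size.** Section 4.0 gives 9,000 adult releases a year, 70% with a qualifying condition, over four years: 9,000 × 4 × 0.70 = 25,200, against a stated figure of about 20,000. The ratio is 20,000/25,200 = 79.4%. The text does not explain the gap; the Medicaid rule or repeat releases could account for it. I use 20,000 below. Nothing turns on the choice.

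**3. Catchment.** Sections 4.0 and 20.2 give 316 + 327 = 643 annual releases at the two sites. 643/9,000 = 7.1%, so about 93% of releases come from places where the pilot does not recruit.

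**4. Calendar overlap.** January 2020 to December 2023 is 48 months. Phase 2 starts in March 2022 (Section 12.0), so 22 months overlap and 26 precede it. With even releases, the overlapping part is 20,000 × 22/48 = 9,167 people.

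**5. Leaving enrollees in.** If all 220 enroll, meet the cohort rules and fall in the window (an upper bound):
- Whole cohort: 220/20,000 = 1.1%. A true 20-point difference would appear as 20 × (1 − 0.011) = 19.8.
- Same-period part: 220/9,167 = 2.4%. It would appear as 20 × (1 − 0.024) = 19.5.

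**6. Illustration for sex mix only.** The spurious difference equals (women's share in pilot − women's share in cohort) × (women's rate − men's rate). The pilot share runs from 120/288 = 41.7% (recruitment capacity, Section 4.0) to 50% (target). The documents give neither other input, so I assume women are 10–20% of the cohort and their 30-day rate is 5–15 points higher.
- Lowest: (0.417 − 0.20) × 5 = 1.1 points.
- Highest: (0.50 − 0.10) × 15 = 6.0 points.

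For scale, the 95% half-width for 220 people at the 34% rate in Section 1.2 is 1.96 × √(0.34 × 0.66/220) = 6.3 points. The 30-day rate is used because it is the only rate given; it is not one of the Section 2.2 secondary endpoints.

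**7. Whether Section 20.4 repairs this.** Its covariates enter models of change over time. With no participant indicator, matching, weighting or standardization described, they do not adjust a participant-versus-cohort difference.

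**The case against.** The plan is modest about this aim. Section 20.1 calls it descriptive, Section 6.1 says there is no control group, and Section 2.1 leaves formal testing to later studies. That limits the claim. It does not make the cohort match the definition in Section 13.1, and Section 20.1 itself still calls the trends a counterfactual.

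Several stronger readings are tempting but not supported:
- A reader might infer that 26 of 48 months (54%) of the comparison is historical. Section 4.0 speaks of concurrent trends and Section 20.4 compares years, so those months are trend history. The gap is that no same-period subset is designated.
- A reader might infer serious contamination by enrollees. In the planned cohort it is 1.1–2.4%. Much larger shares arise only if the comparator is narrowed to the two sites or a few counties, which the plan does not do.
- A reader might infer that outcomes come from different sources, because Section 8.1 lets the team obtain participants' clinic records. But Sections 12.1, 13.4 and 19.1 point to Medicaid data for participants, and the appendix listing secondary-objective data elements is not among the documents. Section 2.2 simply does not name the source.
- A reader might take 1.1–6.0 points as the bias. That range rests on two assumed inputs and on an unadjusted contrast that the plan never specifies.

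It is also fair that the covariates in Section 20.4 could naturally include sex, race and county, and that the nurse's COMPAS review (Section 5.1) may supply an administrative condition flag for participants. Both make the repair easier; neither is yet a stated comparison.

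**Conclusion.** The mismatch is real and can be verified from the text: the group described in Sections 2.1 and 13.1 is not the group constructed in Sections 5.4, 5.5 and 20.3, and Section 20.4 does not define the comparison from which effectiveness would be read. Catchment, entry rules, sex mix and volunteering are the substantive differences; retained enrollees and calendar time are minor or recoverable.

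The net bias cannot be signed or sized from the documents. The month-based counts assume even releases, and the enrollee shares are upper bounds that assume full enrollment. The documents do not support a conclusion that the program's effect will be overstated, or by how much. The point concerns the secondary objective only; the feasibility and acceptability endpoints are unaffected. It should be fixed before the comparison is made.

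**What to change.** (a) **Sections 5.5 and 20.3:** have the programmers with identifier access flag CJC-TraC enrollees and exclude them from the comparator.

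(b) **Section 20.3:** designate releases in the participants' own release period as the comparator for the effectiveness reading, and keep earlier years for trend description. The cohort closes on 12/31/2023 and Phase 2 runs to February 2024, so state how any participant released after the cutoff is handled; there may be none.

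(c) **Section 20.4:** specify one participant-versus-comparator contrast for each Section 2.2 secondary endpoint, with Medicaid claims as the outcome source on both sides. Standardize or adjust at least for sex, race and county of release, and give 95% intervals. Section 20.4 names logistic and Poisson models only, so add a method for days to first visit. Say how participants without Medicaid coverage are counted, since they generate no claims. Report the result as descriptive and not attributable to the program, because volunteering cannot be adjusted away.

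(d) **Sensitivity analysis:** apply the cohort's administrative condition and Medicaid rules to participants, and treat planned carceral discharge alike on both sides where the records allow. Keep this out of the main analysis, because Section 11.1 makes Medicaid enrollment one of the nurse's tasks and conditioning on it selects on an intervention target. Reconcile the Medicaid wording in Sections 5.4, 6.3 and 20.3.

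**Cost:** wording changes, one linkage flag and a little more analysis. Investigators see only masked IDs (Section 8.1) and linking lists are held at WIDOC (Section 23.1), so the flag may need a data-transfer provision. The sensitivity analysis will lose some participants, in a number the documents do not allow one to predict.
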